## MiMP R61 ANALYTIC PLAN

**AIM 1 [R61]: To establish the feasibility and acceptability of the Minds and Mentors Program (MiMP) for individuals on medications for OUD (MOUD; n = 20).**

**Objective 1:** Successfully train counselors and peer mentors, recruit and randomize 20 individuals on MOUD for OUD into the group based MiMP or TSF, and successfully implement the programs within the first two years.

**Hypothesis 1:** Successfully train two counselors and two peer facilitators; the MiMP will demonstrate enrollment, randomization, and retention rates  $\geq 50\%$ ; and  $\geq 50\%$  of participants will positively endorse MiMP as acceptable.

**Objective 2:** Prior to the R33 comparing between-group differences in adherence (primary outcome), we will examine pre- to post-intervention (within-subject) changes in self-reported craving, relapse, stress, anxiety, depression, and social support (secondary outcomes) to determine whether there is preliminary evidence that these outcomes can be improved in those receiving the MiMP.

**Hypothesis 2:** The MiMP will produce reductions in one or more of the following: self-reported stress, cravings, depression, or anxiety, or improvements in perceived social support.

The primary outcome variable is **adherence to MOUD**, quantified as the number of days MOUD was received as indicated during the last 4 weeks of the intervention period. We expect that this can be treated as a continuous variable in regression models. However, prior to modeling we will examine its distribution, to determine if this is appropriate. If, for example, we observe large ceiling effects (many participants report very high or perfect adherence) then we may model non-adherence as the number of days when MOUD was not received. In this case we expect it would have something similar to a Poisson distribution, possibly with over-dispersion which would suggest the use of negative binomial regression. The secondary outcome of **relapse** will be treated in two ways, as a binary indicator if any relapse during the last 4 weeks of the intervention period as determined by UDS or self-report, and the total number of self-reported days of use during the last four weeks of the intervention period. The first dichotomous outcome will require logistic regression. The second approach will depend on the observed distribution and may be treated as either negative binomial or continuous. The other secondary outcome, **cravings**, can be treated as continuous, which will also be true for the ancillary outcomes including depression, anxiety, and stress, are continuous variables.

The table below shows all other secondary measures and the instruments used to measure each of the variables. These instruments are also consistent with data harmonization efforts by the NIH HEAL Initiative. Data collection will happen in accordance with the timeframes stipulated above, T0 - T4. To examine within-subject and between-subject differences from pre to post intervention using repeated measures analysis of covariance (ANCOVA), including covariates, as necessary. Study outcomes will be also be examined using longitudinal regression models, including covariates, as necessary. The full model will include fixed within-subject effects to predict outcomes (stress, depression, anxiety, cravings, self-efficacy, baseline cortisol, cortisol reactivity).

Instrument	Construct	Instrument	Construct
Opioid Craving Scale	Craving	PROMIS Pain Intensity	Pain Intensity
Perceived Stress Scale	Stress	PROMIS Pain Interference	Pain Interference
Generalized Anxiety Disorder 7	Anxiety	PROMIS Pain Catastrophizing	Pain Catastrophizing
Patient Health Questionnaire-9	Depression	Sleep Scale from the Medical Outcomes Study	Sleep
Community Assessment Index	Community Integration	Patient Global Impression of Change	Treatment efficacy
PROMIS Quality of Life	Quality of life	BPI Pain Severity	Pain Severity

**Cortisol Data Analyses:** This type of analysis will also be used in assessment of the cortisol data (i.e., stress reactivity) to examine the effects of treatment on baseline (resting) cortisol levels and cortisol reactivity. Cortisol data is often skewed, so transformations may be performed. The cortisol response will be quantified by calculating the area under the curve (AUC). The trapezoidal formula is given by:

$\sum_{i=1}^5 [t_i(m_i + m_{i+1}) / 2]$ , where  $t_i$  is the interval between sample  $i$  and sample  $i+1$  and  $m_i$  is the level of cortisol for sample  $i$ .

In addition, the influence of pre-treatment cortisol (resting and reactivity) on responsiveness to treatment (as measured by our primary outcome variables) will be examined.

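### Hypothesis 2 credits MiMP with improvement in any one of five outcomes, but is judged on change within the MiMP arm and not tied to the randomised TSF comparison

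*Combined protocol and SAP*

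**What the plan says.** All references are to the MiMP R61 Analytic Plan in the combined protocol and SAP.

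- **Hypothesis 2 (Aim 1):** "The MiMP will produce reductions in one or more of the following: self-reported stress, cravings, depression, or anxiety, or improvements in perceived social support".
- **Objective 2, method:** "we will examine pre- to post-intervention (within-subject) changes in self-reported craving, relapse, stress, anxiety, depression, and social support".
- **Objective 2, purpose:** "to determine whether there is preliminary evidence that these outcomes can be improved in those receiving the MiMP". The same sentence mentions a between-group comparison only for adherence, in the later R33 phase.
- **Objective 1, design:** "recruit and randomize 20 individuals on MOUD for OUD into the group based MiMP or TSF". A concurrent randomised comparator therefore exists, and delivery is in groups.
- **Paragraph on the secondary measures:** "To examine within-subject and between-subject differences from pre to post intervention using repeated measures analysis of covariance (ANCOVA"). The sentence does not define the between-subject contrast as MiMP versus TSF and does not mention Hypothesis 2.
- **Full model, same paragraph:** "The full model will include fixed within-subject effects to predict outcomes (stress, depression, anxiety, cravings, self-efficacy, baseline cortisol, cortisol reactivity"). It does not say whether arm is a term. Social support, one of the five outcomes in Hypothesis 2, is not in the list.
- **Cortisol Data Analyses:** the same type of analysis is to be used "to examine the effects of treatment on baseline (resting) cortisol levels and cortisol reactivity". Here the plan does link the analysis to a treatment effect.

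No alpha, multiplicity rule or definition of success is given for Hypothesis 2.

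**The concern.** Change within one arm can show that the outcomes moved while people received MiMP. It cannot show that MiMP moved them. Participants are on MOUD throughout and receive regular attention, and regression to the mean can lower symptom scores on its own. The TSF arm is there to separate such influences from the programme, but Objective 2 does not use it for this hypothesis.

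The any-of-five rule adds a second, smaller problem: five chances to succeed, with no stated criterion for success. Adjusting for multiplicity would address that problem only, because a non-specific improvement is a real change and a stricter threshold does not remove it.

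What is at stake is a conclusion worded more strongly than its evidence. The plan states no decision that rests on Hypothesis 2.

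**Working it through.** The plan gives no operating figure for Hypothesis 2, so there is nothing to reproduce. The calculations below are illustrations.

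**Inputs from the plan:** 20 randomised in total; five outcomes, any one sufficient; retention target of at least 50%; group-based delivery.

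**Assumptions (not in the documents):** 1:1 allocation, so 10 per arm; two-sided 5% test per outcome, counted only in the favourable direction; outcome correlation 0 to 0.5; no true MiMP effect; non-specific improvement of 0 or 0.3 SD of the change score; where clustering is considered, one or two groups per arm and ICC 0.05 or 0.10.

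**1. Within-MiMP reading, no clustering, n = 10**

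- One outcome, 0.3 SD drift: noncentrality 0.3 × √10 = 0.949 on 9 df, critical value 2.262, giving a probability of 0.134.
- Any of five, independent: 1 − (1 − 0.134)^5 = 0.512. At correlation 0.5 (simulation): 0.380.
- Bonferroni over five: the single-outcome probability is 0.037, and 1 − (1 − 0.037)^5 = 0.172. At correlation 0.5: 0.140.
- No drift: 1 − 0.975^5 = 0.119. At correlation 0.5: 0.095.

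**2. Between-arm reading, no clustering, 10 v 10**

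Any of five favouring MiMP: 0.117 (independent) to 0.094 (correlation 0.5). Drift shared by both arms cancels, so its size does not matter.

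**3. With group effects** (simulation, 100,000 runs, total SD 1, tests ignoring group; ranges run from correlation 0 to 0.5)

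| Groups per arm | ICC | Within MiMP, 0.3 SD drift | MiMP minus TSF |
|---|---|---|---|
| 1 | 0.05 | 63% to 47% | 24% to 18% |
| 1 | 0.10 | 71% to 53% | 35% to 26% |
| 2 | 0.05 | 57% to 42% | 17% to 13% |
| 2 | 0.10 | 62% to 46% | 23% to 17% |

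With no drift and one group per arm, the two readings are about equal: 23% to 17% within MiMP against 24% to 18% between arms at ICC 0.05, and 33% to 24% against 35% to 25% at ICC 0.10 (separate runs, which differ by simulation error). The contrast removes shared drift and nothing else.

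**4. Precision of the contrast, unadjusted for T0**

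- 10 per arm: t(0.975, 18) × √(2/10) = 0.94 SD. With one group per arm, multiply by √(1 + 9 × ICC): 1.13 SD (ICC 0.05) and 1.30 SD (ICC 0.10).
- 5 per arm (the 50% retention floor): t(0.975, 8) × √(2/5) = 1.46 SD. Multiply by √(1 + 4 × ICC): 1.60 and 1.73 SD.
- Coverage of a 95% CI that ignores group, 10 v 10: 89% and 84% with one group per arm (ICC 0.05 and 0.10); 93% and 90% with two.
- Power for a 0.5 SD difference, 10 v 10, independent participants: 18.5%.

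**The case against.** The strongest reply is that the within-subject basis is deliberate. This is a 20-person feasibility phase, Objective 2 asks only for preliminary evidence in MiMP recipients, and the between-group comparison comes later in the R33. That reply justifies the low severity. It does not cure the wording: the R33 comparison is stated for adherence only, and calling evidence preliminary does not turn change over time into an effect of MiMP.

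A second reply is that the link to TSF is implied. The repeated measures ANCOVA sentence covers between-subject differences, the full-model list includes four of the five outcomes, and the cortisol section applies the same type of analysis to treatment effects. This is fair as far as it goes. A between-arm analysis is not absent, and the silence about an arm term is incomplete specification, not a decision to leave arm out. The explicit link to Hypothesis 2 is still missing, and Objective 2 states a different basis.

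Third, the percentages depend on an assumed drift, and without drift the contrast brings no gain in false-positive rate. That is correct. The attribution problem itself does not depend on any of the assumed values.

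Fourth, the contrast changes the question and is imprecise. Both are true and are counted as costs of the fix.

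**Conclusion.** The concern holds, at minor severity. Followed as written, the plan would attribute to MiMP any improvement in its own arm, whatever the cause, although a randomised comparator is available.

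Under the stated assumptions, with 0.3 SD of non-specific improvement and no MiMP effect, Hypothesis 2 is met about 38% to 51% of the time without clustering, and 42% to 71% across the clustered scenarios. Multiplicity adjustment alone leaves 14% to 17% in the unclustered case. The MiMP-minus-TSF contrast is unaffected by shared drift but still carries group effects, so neither reading supports a yes/no verdict from any one of five outcomes.

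Confidence in the textual point is high. The sizes rest on assumed allocation, alpha, drift, outcome correlation, number of groups and ICC.

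**What to change.** - **Analysis.** For each outcome named in Hypothesis 2, report the T0-adjusted MiMP-minus-TSF difference at post-intervention with a 95% CI, and state the arm term in the model. Add social support to the model's outcome list. Report pre-to-post change in each arm as descriptive.
- **Wording.** Replace Hypothesis 2 with, for example: *We will estimate the T0-adjusted MiMP-minus-TSF difference in stress, cravings, depression, anxiety and perceived social support, with 95% CIs, as preliminary evidence; change within each arm is descriptive.* Give no supported/not-supported verdict from any one of the five.
- **Context for the estimates.** The plan says "Successfully train two counselors and two peer facilitators" but the text available does not say how they are divided between programmes. Unless this is stated elsewhere, give that division and the number of groups per arm beside the results. With one group per arm, say that the difference cannot be separated from group and facilitator.

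**Cost.** SAP wording, one model term and one added outcome; no new data. Four downsides should be accepted openly:

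1. The intervals are wide.
2. With one group per arm the group effect cannot be estimated, so an interval that ignores it covers less than its nominal 95%.
3. The contrast is relative to another delivered programme. It answers a different question from improvement under MiMP and is less likely to look favourable.
4. Power is low, so the result should be presented as a preliminary estimate and not as a test.

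### The primary adherence model names no baseline adherence value for people already on MOUD, which gives up precision that a T0 look-back item could recover

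*Combined protocol and SAP*

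**What the plan says.** Aim 1, Objective 1 of the MiMP R61 Analytic Plan is to "recruit and randomize 20 individuals on MOUD for OUD into the group based MiMP or TSF". Participants are therefore on treatment when they are randomized.

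The outcome paragraph takes adherence as primary: "The primary outcome variable is adherence to MOUD, quantified as the number of days MOUD was received as indicated during the last 4 weeks". That window closes the program. On the model it says: "We expect that this can be treated as a continuous variable in regression models". If many participants turn out to be at or near perfect adherence, the plan may instead count non-adherent days with a Poisson-type or negative binomial model. Neither form has a named covariate.

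Two later sentences bear on adjustment. One concerns pre-to-post differences: "To examine within-subject and between-subject differences from pre to post intervention using repeated measures analysis of covariance (ANCOVA), including covariates, as necessary". The other is general: "Study outcomes will be also be examined using longitudinal regression models, including covariates, as necessary". The sentence that follows lists outcomes, and adherence is not among them: "The full model will include fixed within-subject effects to predict outcomes (stress, depression, anxiety, cravings, self-efficacy, baseline cortisol, cortisol reactivity".

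Objective 2 places the between-group comparison of adherence in the R33. Its list of R61 pre-to-post outcomes does not include adherence.

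**The concern.** For people already on MOUD, adherence before randomization is the obvious candidate predictor of adherence at the end of the program. The definition covers only the final 4 weeks, and the model names no entry value.

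The general covariate clause permits adjustment but does not say for what, in which model, or on what criterion. With 20 participants, an adjustment chosen after the data are in can move the estimate noticeably, and the reader cannot tell whether it was chosen for that reason.

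What is at stake is efficiency and credibility. An unadjusted contrast is noisier than it need be. In any single small trial it can also be shifted by arms that happened to differ at entry, with no pre-specified way to take that out.

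**Working it through.** The plan gives no power, effect size, standard deviation or correlation for adherence, so there is no figure of its own to reproduce. What follows is an illustration.

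**Input from the plan:** 20 randomized participants in two arms (Objective 1).

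**Assumptions not in the plan:** 10 per arm, no dropout, a linear model with a normal outcome, and a baseline-to-end correlation r of 0.3, 0.5 or 0.7. Baseline and end adherence are each in SD units.

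**1. Chance imbalance at entry.** The SD of the between-arm difference in mean baseline adherence is sqrt(1/10 + 1/10) = 0.447 SD. The 95% range is ±1.96 × 0.447 = ±0.88 SD. The probability of an imbalance above 0.5 SD in either direction is 0.26.

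**2. Effect on the unadjusted contrast.** An imbalance d shifts the end-of-intervention difference by r × d. For d = 0.447 SD:
- r = 0.3: 0.13 SD
- r = 0.5: 0.22 SD
- r = 0.7: 0.31 SD

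**3. Gain from adjustment.** The residual variance is multiplied by 1 − r². An approximate allowance for the lost degree of freedom (18 to 17) is 18/17 = 1.059.

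| r | 1 − r² | × 18/17 |
|---|---|---|
| 0.3 | 0.91 | 0.96 |
| 0.5 | 0.75 | 0.79 |
| 0.7 | 0.51 | 0.54 |

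Using the expected inflation for one normal covariate, 1 + 1/16, gives 0.97, 0.80 and 0.54, so the choice of allowance hardly matters.

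**4. Check by simulation under no effect** (10,000 replicates for each r, with r = 0.8 added). The unadjusted analysis had a mean effect between −0.003 and 0.003 SD and a type I error between 0.044 and 0.053. It is therefore unbiased and keeps its level. The SD of the estimate, unadjusted then adjusted, was:
- r = 0.3: 0.440 and 0.433, variance ratio (0.433/0.440)² = 0.97
- r = 0.5: 0.449 and 0.403, ratio 0.81
- r = 0.7: 0.448 and 0.331, ratio 0.55

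These agree with step 3.

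**5. Carrying this to the R33.** Its sample size is not given in the text. With more participants the imbalance in step 1 shrinks, but the factor 1 − r² does not depend on sample size. The proportional precision gain would therefore remain.

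**The case against.** The strongest reply is that the R61 does not rest on this comparison. Its hypotheses concern training, enrollment, randomization, retention, acceptability and change in secondary outcomes, and the adherence contrast belongs to the R33. That is right, and it lowers the urgency. It does not remove the point, because the outcome paragraph sets out the adherence model in this plan without limiting it to the R33, and a baseline item is best defined before it is needed.

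A second reply is that the covariate clauses already allow the adjustment. They do, but permission is not specification.

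A third is that the size rests on an assumed correlation and a linear model, while the plan itself foresees a ceiling and a switch to a count model. This also stands. The figures above do not cover that case, and if nearly everyone is fully adherent at entry, a baseline value carries little information.

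A reader might also infer four stronger claims that the documents do not support:
- **That there is no limit on time on MOUD.** The available text has no eligibility section, so silence there shows nothing.
- **That adherence is measured only at the end.** The text fixes the window of the primary outcome and does not say that adherence goes unrecorded at T0. The T0–T4 schedule is not in the available text. The instrument table covers the remaining secondary measures, so a primary outcome would not be expected in it.
- **That entry differences pass straight into the comparison.** Randomization balances them in expectation, and only the fraction r of a chance imbalance carries over.
- **That a noisy R61 adherence estimate will be used to plan the R33.** Nothing in the text says so.

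**Conclusion.** The point holds as a cheap improvement. The plan defines its primary outcome over an end-of-intervention window, in people who already have an adherence level, and pre-specifies no baseline value or covariate for the model.

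This is not a source of bias. The cost is precision, plus exposure to chance imbalance in a given trial. With an assumed 10 per arm and a linear model, the variance of the contrast would fall by about 4%, 21% or 46% for r = 0.3, 0.5 or 0.7. The gain is negligible at the low end and substantial at the high end. The plan gives no basis for choosing r, and no gain has been calculated for the count model or under a strong ceiling.

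**What to change.** - **Baseline measure.** At T0, unless it is already collected, record adherence over a pre-randomization look-back of up to 28 days. Express it as the proportion of days on MOUD on which it was received as indicated, so that recent starters and established patients are on one scale.
- **Model.** Name this proportion as a fixed covariate in the primary adherence model, in both its continuous and its count form.
- **Timing.** Write this into the plan before the between-group adherence comparison planned for the R33.

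The cost is one look-back item at T0 and one degree of freedom. For recent starters the look-back is shorter, so their baseline is noisier. If T0 adherence is already recorded, a sentence defining the covariate is enough.

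### Binary relapse is assigned to logistic regression in at most 20 people with no sparse-data form, so any between-arm odds ratio fitted by ordinary maximum likelihood may not be finite

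*Combined protocol and SAP*

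**What the plan says.** All references are to the MiMP R61 Analytic Plan in the combined protocol and SAP.

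- **Size and arms.** Aim 1, Objective 1 is to "recruit and randomize 20 individuals on MOUD for OUD into the group based MiMP or TSF". No allocation ratio is given.
- **Retention.** Hypothesis 1 says "the MiMP will demonstrate enrollment, randomization, and retention rates" of at least 50%.
- **Outcome.** The paragraph on outcome variables treats relapse first "as a binary indicator if any relapse during the last 4 weeks of the intervention period as determined by UDS or self-report", and second as self-reported days of use over the same 4 weeks.
- **Model.** For the binary form, "The first dichotomous outcome will require logistic regression". Days of use may be negative binomial or continuous, depending on its distribution. Adherence also has a distribution-dependent alternative. Binary relapse has none.
- **Contrast.** Objective 2 says "we will examine pre- to post-intervention (within-subject) changes in self-reported craving, relapse" and other outcomes. The analysis text also plans to examine "within-subject and between-subject differences from pre to post intervention using repeated measures analysis of covariance (ANCOVA), including covariates, as necessary", and adds: "Study outcomes will be also be examined using longitudinal regression models, including covariates, as necessary". Neither sentence names relapse, and the logistic sentence names no contrast.

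**The concern.** With 20 people in two arms, a binary outcome can easily have an empty cell. Ordinary maximum likelihood then has no finite arm coefficient: the estimate drifts for as long as the software iterates, and the Wald interval and p-value mean nothing. If both arms have no relapses, the odds ratio is not identified at all.

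Failure also need not be neutral. If MiMP truly lowers relapse, the arm most likely to have no relapses is MiMP, so the trials lost to the model are mainly those that look best for it. Choosing a replacement method after a zero cell has been seen is the kind of data-led decision that a plan should prevent.

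**Working it through.** **Inputs.** From the documents: 20 people, two arms, and a retention threshold of at least 50%. Assumed: 1:1 allocation and every relapse rate. The plan has no figure of its own to reproduce. Three analysis sets are used:
- 10 per arm: full retention.
- 5 in MiMP and 10 in TSF: the 50% threshold applied to MiMP, the programme it is stated for.
- 5 per arm: the same threshold in both arms, as a worst case.

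**Step 1: chance of no finite odds ratio (arm-only model).** With relapse probabilities p1, p2 and arm sizes n1, n2:

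P = 1 − (1 − [(1−p1)^n1 + p1^n1]) × (1 − [(1−p2)^n2 + p2^n2])

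At 20% in MiMP and 40% in TSF:
- 10 per arm: 0.8^10 + 0.2^10 = 0.1074 and 0.6^10 + 0.4^10 = 0.0062, so P = 1 − 0.8926 × 0.9938 = 0.113.
- 5 per arm: 0.8^5 + 0.2^5 = 0.3280 and 0.6^5 + 0.4^5 = 0.0880, so P = 1 − 0.6720 × 0.9120 = 0.387.

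| Relapse rate | 10 v 10 | 5 v 10 | 5 v 5 |
|---|---|---|---|
| 10% both | 58% | 73% | 83% |
| 20% both | 20% | 40% | 55% |
| 30% both | 5.6% | 19% | 31% |
| 50% both | 0.4% | 6.4% | 12% |
| 20% v 40% | 11% | 33% | 39% |

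**Step 2: direction of the failures.** Summing over all failing tables at 20% against 40%, the lower relapse proportion is in MiMP in 95% of them with 10 per arm and in 80% with 5 per arm.

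**Step 3: what the software returns.** For 0/10 against 4/10, the log odds ratio is −10.8 (SE 86) after 10 iterations, −21.0 (SE 14,185) after 20 and −31.4 (SE about 2.5 million) after 35. It does not converge.

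**Step 4: whether days of use is a backup.** If nobody in an arm relapses by urine drug screen or self-report, that arm's self-reported days are all zero. A negative binomial model with a log link then has no finite rate ratio. For days 0, 0, 0, 0, 0 against 0, 0, 0, 4, 9, with dispersion set to 1, the log rate ratio is −6.4, −11.4 and −21.4 after 5, 10 and 20 iterations (SE 4, 50 and 7,411). Only the continuous option avoids this.

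**Step 5: how the alternative behaves.** With arm only, Firth's estimate equals adding 0.5 to each cell. For 0/5 against 2/5, which has probability 0.3277 × 0.3456 = 11% at 20% against 40%, the odds ratio is (0.5 × 3.5)/(5.5 × 2.5) = 0.13, with a 95% profile interval of 0.0008 to 2.2. The risk difference is −40 points, Newcombe 95% interval −77 to +12.

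Over all trials at 20% against 40%, where the true log odds ratio is ln[(0.2/0.8)/(0.4/0.6)] = −0.98:

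| | 10 v 10 | 5 v 10 | 5 v 5 |
|---|---|---|---|
| Firth mean log odds ratio | −0.97 | −0.87 | −0.88 |
| Firth RMSE | 1.02 | 1.10 | 1.27 |
| Newcombe coverage | 94.4% | 95.9% | 95.9% |
| Newcombe mean width (points) | 69 | 80 | 89 |

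Firth's shrinkage towards no effect is therefore 0.01, 0.11 and 0.10 on the log scale, which is small beside the RMSE.

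**The case against.** The strongest reply is that no stated analysis is shown to fail. Objective 2 frames R61 relapse as within-subject change and leaves the between-group adherence comparison to the R33. The between-subject wording sits in the ANCOVA sentence, not the logistic one. This stands. A reader might infer that the plan commits to a between-arm relapse odds ratio; it does not, and the figures above apply only if one is fitted. The within-subject reading does not remove the difficulty, however. With 1:1 allocation it leaves about 10 people in MiMP, where sparse cells are again possible, although no failure rate was calculated for that model.

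A second reply is that Firth and exact fits are themselves logistic regression, so the plan does not exclude them. That is correct: the gap is that no form is chosen, not that a wrong one is mandated.

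A third is that the failure chance runs from 0.4% to 83% on assumptions alone. That also stands. If relapse is common and retention is full, the problem is rare. A failed fit would also be visible, and counts could still be reported.

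A reader might also infer that pre-to-post change in relapse has no baseline, since both relapse variables are defined only for the end of the intervention. The documents do not support that conclusion. The plan says "Data collection will happen in accordance with the timeframes stipulated above, T0 - T4", and the schedule it points to is not in the available text, so a baseline measure may exist.

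**Conclusion.** The point holds as a conditional one. For any between-arm analysis of binary relapse by ordinary maximum likelihood, the chance of no finite odds ratio at an assumed 20% against 40% is 11% with 10 per arm and 39% with 5 per arm. It is higher at low relapse rates and negligible at 50% with full retention. These figures rest on assumed relapse rates, 1:1 allocation and the retention scenarios.

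The importance is low. Relapse is a secondary outcome in a feasibility phase, and neither Hypothesis 2 nor the feasibility criteria use it. The documents do not support a claim that the R61 conclusions are at risk. The change is still worth considering, because it is cheap and fixes the method before any zero cell is seen.

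**What to change.** Amend the SAP wording:

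1. State the contrast for the binary relapse model.
2. For any between-arm analysis, use Firth penalised or exact logistic regression with arm as the only term. Report counts per arm and the risk difference with a Newcombe or exact interval, as estimates and not as a test.
3. If days of use is all zero in an arm, report the difference in mean days with an interval instead of a rate ratio.
4. Report within-MiMP pre-to-post change in binary relapse as paired counts, if a comparable baseline measure exists.

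The cost is a few sentences and no new data. The downsides are very wide intervals (Newcombe mean width 69 to 89 points in the scenarios above) and p-values that depend on the method: for 0/10 against 4/10, Firth gives 0.031 and Fisher's exact test 0.087. That disagreement is the reason to report estimates only.

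### MiMP is delivered in groups, but no analysis named in the R61 plan allows for correlation among members of the same therapy group

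*Combined protocol and SAP*

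**What the plan says.** Objective 1 of Aim 1 sets out to "recruit and randomize 20 individuals on MOUD for OUD into the group based MiMP or TSF". This makes MiMP group based; whether the adjective also covers TSF is not clear from the wording.

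Objective 2 looks at "pre- to post-intervention (within-subject) changes in self-reported craving, relapse, stress, anxiety, depression, and social support" in people receiving MiMP. The between-arm adherence comparison is placed in the later phase: "Prior to the R33 comparing between-group differences in adherence (primary outcome").

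For the secondary measures, the Analytic Plan names two approaches. One is "To examine within-subject and between-subject differences from pre to post intervention using repeated measures analysis of covariance (ANCOVA"). The other is given as: "Study outcomes will be also be examined using longitudinal regression models, including covariates, as necessary". Relapse is to be analysed partly "as a binary indicator if any relapse during the last 4 weeks of the intervention period", by logistic regression. Adherence, and days of use, may be modelled as continuous or by negative binomial regression. Under Cortisol Data Analyses the plan adds: "This type of analysis will also be used in assessment of the cortisol data".

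**The concern.** People in one therapy group share leaders, sessions and peers, so their changes may resemble one another more than those of people in different groups. If so, ten people in one or two groups carry less information than ten people treated separately. A model with no term for the group gives standard errors that are too small.

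Two R61 results are exposed. The first is the MiMP pre-post change, which Objective 2 uses to judge whether the secondary outcomes look improvable. The second is any between-arm difference reported in the R61, since the repeated measures ANCOVA is also meant to look at between-subject differences. In both, the reader would see tighter intervals than the data support.

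**Working it through.** **Step 1. Read each named analysis for an allowance for therapy group.**

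| Outcome | Analysis named | Therapy-group allowance |
|---|---|---|
| Adherence | Linear regression, or Poisson/negative binomial for days missed | None named |
| Relapse | Logistic (any relapse); negative binomial or continuous (days of use) | None named |
| Craving, stress, anxiety, depression and other scales | Repeated measures ANCOVA; longitudinal regression | None named |
| Cortisol | Same type of analysis | None named |

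The full model is described only by fixed within-subject effects. The provision for covariates does not mention therapy group.

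**Step 2. Inputs.** The documents give 20 randomized. They give no allocation ratio, group size, number of groups, ICC, significance level or confidence level, so there is no planned figure to reproduce. Assumed for illustration: 10 in MiMP, closed groups, no dropout, normally distributed change scores, a nominal 95% t interval, and a change-score ICC of 0.01, 0.05 or 0.10.

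**Step 3. One group of 10, exactly.** The mean has variance σ²[ICC + (1 − ICC)/10], but the sample variance estimates only σ²(1 − ICC). The true variance of the mean is therefore 1 + 10·ICC/(1 − ICC) times the one used, and

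coverage = 1 − 2·P(t₉ > 2.262 / √(1 + 10·ICC/(1 − ICC))).

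At ICC 0.05 the factor is 1 + 0.5/0.95 = 1.526, its root is 1.235, and 2.262/1.235 = 1.83. Coverage is 90.0%. At ICC 0.01 and 0.10 it is 94.1% and 84.6%.

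**Step 4. Other layouts, by simulation of a null arm.** Widening uses √D with D = 1 + (m − 1)·ICC, where m is the size-weighted mean group size. For groups of 7 and 3, m = (49 + 9)/10 = 5.8. Entries are for ICC 0.01 / 0.05 / 0.10.

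| MiMP layout | Coverage, unadjusted (%) | √D | Coverage after widening (%) |
|---|---|---|---|
| Two groups of 5 | 94.6 / 92.8 / 90.5 | 1.020 / 1.095 / 1.183 | 95.0 / 94.8 / 94.5 |
| Groups of 7 and 3 | 94.5 / 92.4 / 89.6 | 1.024 / 1.114 / 1.217 | 95.0 / 94.8 / 94.5 |
| One group of 10 | 94.1 / 90.0 / 84.6 | 1.044 / 1.204 / 1.378 | 94.9 / 94.5 / 94.0 |

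Read as a two-sided 5% test, unadjusted type I error runs from 5.4% to 9.5% with two groups of 5, and from 5.9% to 15.4% with one group of 10.

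**Step 5. Dropout.** If half the arm is lost and groups of 3 and 2 remain (assumed), unadjusted coverage is 94.9% / 94.3% / 93.5%.

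**Step 6. Between-arm interval for a continuous outcome, 10 per arm, ICC 0.05.** With both arms grouped, coverage is 92.6% (two groups of 5) or 89.4% (one group of 10). With only MiMP grouped, it is 93.8% or 92.3%. Multiplying the variance of each grouped arm by D brings these to between 94.5% and 94.9%.

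**Step 7. Does the multiplier carry over to binary relapse?** For a logistic comparison with 10 per arm, two groups of 5, an assumed relapse rate of 40% and ICC 0.05, the unadjusted interval already covers about 95.0%. Multiplying the variance by D takes it to 98.5%. The multiplier over-corrects here, so it should be confined to continuous outcomes.

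**The case against.** A reader might infer that the plan specifies independence between group members. It does not. It names model families in a line each, states no covariance structure, and a longitudinal model could carry a group effect. The supportable statement is conditional: if the models are fitted as named, without a group term, the intervals ignore clustering. The plan also refers back to assessment timeframes set out in text outside the document reviewed here, and delivery format or a clustering provision could be described there too. The point is limited accordingly.

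It can fairly be said that no stated R61 decision depends on this. Hypothesis 1 uses training targets and 50% thresholds, and the plan sets no significance level. Clustering may not even be the largest issue for Objective 2. Hypothesis 2 is met by improvement in any one of five outcomes. If each were tested at 5% and they were independent (both assumed), the chance of at least one false positive would be 1 − 0.95⁵ = 22.6%, above the worst single-test figure of 15.4%. That puts the effect in proportion but does not remove it, since every one of those intervals would still be affected.

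The objections that the size rests on assumed inputs, shrinks with dropout, and was shown only for t intervals all stand. The last is why the fix leaves logistic and negative binomial outcomes out of the variance adjustment.

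**Conclusion.** The point holds in limited form. MiMP is group based, and no named analysis allows for correlation within a therapy group. The resulting error is in the width of the Objective 2 intervals and of any R61 between-arm interval, and it arises only if within-group correlation is positive. On the stated assumptions it ranges from negligible (ICC 0.01, groups of 5) to a loss of about ten percentage points of coverage (ICC 0.10, one group of 10).

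Two larger conclusions might be inferred and are not supported. The feasibility and acceptability criteria are not undermined, because they do not rest on these intervals. Nor does this show that the R33 adherence comparison is mis-analysed or too small: its plan is not in the document, and no claim is made about it. The R61 consequence is modest, but the correction is cheap and group membership is best recorded as it happens.

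**What to change.** - Record a therapy-group ID for each participant in a group-delivered arm, and state whether TSF is one.
- Keep the planned analyses, and label their intervals as ignoring clustering.
- For the continuous Objective 2 outcomes (craving, stress, anxiety, depression, social support), and for any between-arm difference in a continuous outcome that the R61 reports, add one sensitivity interval at the low end and one at the high end of a stated, assumed ICC range. Multiply the variance of each group-delivered arm by 1 + (m − 1)·ICC, with m the size-weighted mean group size among those analysed.
- For relapse and other outcomes analysed by logistic or negative binomial models, do not apply the multiplier. Report the result by therapy group and state that clustering is not accounted for.
- If only one group runs per arm, state that arm and group effects cannot be separated.

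A clustered model is not required at n = 20.

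The cost is one variable, a few sentences in the plan and about ten extra intervals (five outcomes at two ICC values), plus two for each between-arm difference reported. Over ICC 0.01 to 0.10 the sensitivity intervals are wider by about 2% to 18% with groups of 5, or 4% to 38% with one group of 10. They rest on an ICC that has to be assumed.
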